## **IV. Research Methods**

### **A. Outcome Measure(s):**

#### **Main study:**

##### **Primary:** Feasibility and acceptability:

- We will assess the ease of recruiting women for the study (number enrolled/number approached) and attrition from the study.
- We will also collect data on intervention adherence, including number of women who received the entire intervention, number of women who came to visits, use of HeartSmartMoms (HSM), participation in self-monitoring, use of phone coaching, and use of the Facebook group page.

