### **B. Description of Population to be Enrolled:**

#### **Main study:**

We will be working with low-income, English or Spanish-speaking postpartum mothers enrolled in the Aurora WIC clinic. The Aurora WIC clinic serves predominantly minority women; nearly 70% of women are racial/ethnic minorities. To be eligible for WIC, women must be low-income or  $\leq 185\%$  of the poverty level.

This population was chosen because they are at high risk for obesity in the postpartum period and weight retention and prolonged obesity.

Inclusion criteria:

- Adult woman ( $\geq 18$  and  $< 50$  years old)
- Enrolled in WIC or with an infant enrolled in WIC;
- 3-12 months postpartum
- A pre-pregnancy BMI of 25 - 40 kg/m^2 (based on self-reported height and weight prior to pregnancy)
- Postpartum body mass index between 25 and 50 kg/m^2
- English- and/or Spanish-speaking
- Owns a mobile phone with texting functionality
  - In order to receive texts during the trial

Exclusion criteria:

- Health conditions impacting weight or ability to participate in a weight loss trial
  - Pregnancy or planned pregnancy in next 5 months
  - Any health problems or undergoing any treatments that might interfere with what participant eats or her ability to exercise
  - Medical provider recommendation to avoid exercise
- Plans to be in a different geographic area within the next 5 months
- Plans to stop coming to Aurora WIC in the next 5 months.
- Unable to give informed consent;
- Not able to read and understand English or Spanish at an 8th grade level.
- Not willing to create a Facebook account if they do not already have one.
- Asked to follow-up in  $< 3$  months at most recent WIC visit

Substudy:

The substudy will have 2 parts – Part A and B. Part A applies to the lifestyle group from the main study and will have 2 phases (1 and 2). This is split into 2 phases so that Phase 2 opportunity and the associated financial remuneration of Phase 2, is not known until the 12 week visit. We want a true assessment of the participation in the lifestyle intervention as it would be run in WIC, and thus do not want participants to stay in the intervention solely for the remuneration in the substudy. Part B applies to the observation group in the main study.

Part A Phase 1

Inclusion criteria:

- Participant in the lifestyle group in the Main study presenting for baseline visit

Exclusion criteria:

- None

Part A Phase 2

Inclusion criteria:

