## C. Study Design and Research Methods

Main study: We propose a pilot randomized controlled trial. We will pilot a multicomponent intervention delivered in a WIC setting. In order to attempt to model the intervention as it would be run in WIC, there will be no remuneration for participating other than the small gift (\$5) at the beginning of the study.

Substudy: Women in the main study will be eligible for this substudy. The substudy is broken into 2 Parts (A-Lifestyle group from Main study , B- observation Group from Main study). We will ask participants to complete a survey and for some a semi-structured interview.

Here is an overview of our study process

**Setting:** The study (main and substudy) recruitment/enrollment, intervention delivery and data collection will occur at the Aurora WIC clinic. Over a year ago we partnered with WIC and over the last year developed this study protocol together, with input from WIC clients. All study activities will occur at this site except for data management, some phone/text contact with interested individuals/participants, and data analysis.

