### Substudy:

The substudy will be broken into 2 parts: Part A for Lifestyle group participants and Part B for the Observation group participants. Data collection varies slightly between these 2 groups as outlined in the study procedures. Only persons participating in the Main study are recruited to be in the Substudy. Screening for eligibility will be done by the PRA based on assigned group in the Main study. Enrollment will occur as follows:

Part A for lifestyle group involves completing 2 phases.

Part A: Phase 1 (labeled Part A.1) involves survey data collection around the time of the Main study's Baseline visit. This will occur either at the visit when the person is consented into the main study or at the baseline visit. After the person is consented into the main study and randomized to the lifestyle group, they can then complete data collection for the main study. Once this is done, they will then be offered the opportunity to participate in this substudy. If they are interested, the RA will conduct informed consent using the information sheet Appendix F.A.1.

Part A: Phase 2 (labeled Part A.2) involves survey and interview data collection at the Main study's 12 week visit. After completing data collection for the Main study at the 12 week visit, the PRA will introduce this study opportunity. If the person is interested, the RA will then complete informed consent, using the information sheet Appendix F.A.1., and enroll the person into the study.

These 2 phases will be presented to participants at these different time points in order to ensure that the substudy opportunity is not an incentive to participate in the main study.

Part B for the observation group involves survey data collection at both the baseline and 12 week visit. This substudy opportunity for data collection at 2 time points will be offered to participants at the baseline visit. If the person is interested, the RA will then complete informed consent, using the information sheet Appendix F-B, and enroll the person into the study.

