- a. Diet Survey: We will use the Block Fat/Sugar/Fruit/Vegetable Screener which takes 10-12 minutes to complete and is available in English and Spanish. This is a publically available questionnaire. This screener contains 55 questions. Portion size is asked for 32 food items. A series of "adjustment" questions ask about usual intake of low-fat/trans-fat free or low-carbohydrate/low-sugar versions of various foods. Analysis produces estimates of saturated fat, trans fat, total sugars, "added sugars" (in sweetened cereals, soft drinks, and sweets), fruit and fruit juice, vegetable intake, glycemic load and glycemic index. The bilingual research assistant will orally administer this. Data will provide estimates on dietary saturated fat, trans fat, total sugars, "added sugars" (in sweetened cereals, soft drinks, and sweets), fruit and fruit juice, vegetable intake, glycemic load and glycemic index. The Block booklets will be mailed to the company for analysis. The only identifier on each booklet will be the participant study ID number.
- b. Pregnancy Physical Activity Questionnaire: We will use a slightly adapted version of the Pregnancy Physical Activity Questionnaire (PPAQ) Chasan-Taber L, Schmidt MD, Roberts DE, Hosmer D, Markenson G, Freedson PS. Development and Validation of a Pregnancy Physical Activity Questionnaire. Med Sci Sports Exer 2004 36(10):1750-1760.
- c. Self-efficacy regarding diet and exercise: some items are from another study (unpublished) and some are from [http://sallis.ucsd.edu/measure\\_selfefficacy.html](http://sallis.ucsd.edu/measure_selfefficacy.html)
- d. Eating Stimulus Index: <http://europepmc.org/abstract/med/19699840>
- e. Readiness to Change: Items are from another study

Participants from the observation group will receive at the 12 week visit a \$50 gift card for their participation.

Overview of data collection:

Data to be collected from study participants and when the data are to be collected

Variable	Baseline Visit 1	4 week visit (Lifestyle group only)	8 week visit (Lifestyle group only)	12 week visit
Main study				
Demographics Questionnaire	X			

Smoking status	X			X
Breastfeeding history	X			X
Health questions	X			X
Weight	X	X	X	X
Height	X			
Substudy				
Block Fat/Sugar/Fruit/Vegetable Screener	X			X
Pregnancy Physical Activity Questionnaire	X			X
Self-efficacy re: diet and exercise	X			X
Eating Stimulus Index	X			X
Perceived Stress Scale	X			

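### Does paying observation-arm women at week 12, while the lifestyle arm's week-12 payment is kept undisclosed, undermine attrition as a feasibility outcome?

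*Combined protocol and SAP*

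**What the plan says.** Section IV.A (Outcome Measures, Main study, Primary) lists recruitment and attrition in one line: "number enrolled/number approached) and attrition from the study". Section IV.F (Data Analysis Plan, Aim 1) repeats it. Neither place names an arm, a denominator or a time point. Both then list separate adherence measures, including receipt of the full programme, visit attendance, self-monitoring, phone coaching and Facebook use.

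The substudy pays the arms differently.

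- **Observation arm (Part B).** Section IV.C, Substudy enrolment: "This substudy opportunity for data collection at 2 time points will be offered to participants at the baseline visit". The only Part B payment stated is at the end: "Participants from the observation group will receive at the 12 week visit a" 50-dollar gift card. The same visit supplies the main-study 12-week weight.
- **Lifestyle arm (Part A).** Women receive 25 dollars for the baseline survey and 35 dollars for the week-12 survey and interview. Section IV.B says Part A is split "so that Phase 2 opportunity and the associated financial remuneration of Phase 2, is not known until the 12 week visit", and gives the reason: "We want a true assessment of the participation in the lifestyle intervention as it would be run in WIC". Section IV.C adds, with main-study participation in mind: "These 2 phases will be presented to participants at these different time points in order to ensure that the substudy opportunity is not an incentive".

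The main study itself pays nothing beyond a small baseline gift: "In order to attempt to model the intervention as it would be run in WIC, there will be no remuneration for participating".

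**The concern.** The protocol argues that a known week-12 payment would distort retention, and it withholds that payment from the lifestyle arm for this reason. It then tells observation women who join Part B, apparently from baseline, about a payment at the visit that decides whether they count as lost. A single study-wide attrition figure would mix an arm shielded from the incentive with an arm exposed to it, and would make retention look better than it is for the intervention. Section IV.G rests the case for a larger trial on feasibility and acceptability, so a flattering figure could matter.

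There is a second route to harm. The weight comparison is a t-test on change from baseline to week 12, with no stated handling of missing weights. If payment makes return differ between arms, the women compared may differ too.

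**Working it through.** **What the documents supply.** They give 20 women per arm (up to 80 in all, so 40 per arm) and payments of 25 + 35 = 60 dollars (lifestyle) and 50 dollars (observation). They give no expected attrition, Part B uptake, payment effect or SD of weight change, so there is no planned figure to reproduce. The rates below are assumptions.

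**1. Effect on a pooled attrition figure.** With equal arms, payment lowers pooled attrition by 0.5 × uptake × effect among joiners.

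| Part B uptake | Effect on return | Fall in pooled attrition |
|---|---|---|
| 50% | 10 points | 0.5 × 0.5 × 10 = 2.5 points |
| 50% | 20 points | 0.5 × 0.5 × 20 = 5 points |
| 100% | 20 points | 0.5 × 1.0 × 20 = 10 points |
| 100% | 30 points | 0.5 × 1.0 × 30 = 15 points |

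For example, suppose both arms would lose 40% without payment. At 50% uptake and a 20-point effect, observation attrition becomes 30% and the pooled figure 35%. The lifestyle figure stays at 40%. If payment has no effect on return, it distorts nothing.

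**2. Precision.** A lifestyle attrition of 8/20 has a Wilson 95% interval of 22% to 61%; 16/40 gives 26% to 55%. A 5-point shift is small beside either interval.

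**3. Effect on the weight comparison.** Suppose women who lose more weight are likelier to return, with correlation r between weight loss and the tendency to return. If a proportion p returns, mean loss among returners is inflated by r × SD × L(p), where L(p) = φ(z_p)/p. This gives L = 0.644, 0.497 and 0.350 at p = 0.60, 0.70 and 0.80. Take r = 0.3 and SD 3 to 5 kg.

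| Lifestyle return | Observation return | Spurious difference (positive favours lifestyle) |
|---|---|---|
| 60% | 70% | 0.3 × (3 to 5) × (0.644 − 0.497) = 0.13 to 0.22 kg |
| 60% | 80% | 0.3 × (3 to 5) × (0.644 − 0.350) = 0.26 to 0.44 kg |
| 80% | 60% | −0.26 to −0.44 kg |
| 80% | 80% | 0 |

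For the first two rows the bias divided by its standard error is 0.11 and 0.23 with 20 per arm, and 0.16 and 0.33 with 40 per arm. The noncentral t distribution then gives a two-sided false-positive rate of 5.1% and 5.6% (20 per arm), or 5.3% and 6.2% (40 per arm).

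The last two rows matter most. If the lifestyle programme itself holds women better, the bias exists without any payment, and a payment that lifts observation return to 80% removes it.

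**4. What attrition is needed for.** Section IV.E says heavy attrition could make Aim 2 impossible. Aim 2 compares both arms, so control-arm retention also bears on feasibility, namely of the trial. The activity table in IV.C puts intervention visits at baseline and weeks 4 and 8; week 12 is data collection. Uptake of the intervention is therefore measured by the adherence counts, which come from the lifestyle arm and do not depend on the 50 dollars.

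**5. The completer goal.** The recruitment section of IV.C aims for 40 substudy completers in total, and the sample-size paragraph of IV.F gives 20 and 20. These are compatible. A pooled stop at 40 completers, with 60% v 80% completion, would leave fewer than 20 lifestyle completers in 91% of simulated trials. But the plan states no such stopping rule, and equal 60% completion in both arms already gives 41%.

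**The case for a change.** The strongest case for a change is that attrition belongs to the primary outcome and should be pinned down before the data are seen. With no arm, denominator or threshold, the team could choose the more favourable presentation, and the protocol's own reason for hiding the lifestyle payment shows it thinks payment matters. A one-line definition would cost almost nothing.

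Part of this stands. The definition is unwritten, and a pooled figure, if someone reported only that, would be hard to interpret. The rest is weaker. The plan sets no attrition threshold that a pooled figure could be made to pass. Its stated reasons for withholding payment concern the lifestyle programme and Part A, so it breaks no rule of its own.

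The asymmetry is also partly inferred. That observation women know of the 50 dollars in advance follows only from when they consent. That lifestyle women do not know of Phase 2 rests on stated intent: Phase 2 consent is taken "using the information sheet Appendix F.A.1., and enroll the person into the study", the same sheet named for Phase 1, and its contents are not in the supplied text.

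A hasty definition can also mislead. Counting every randomised woman without a 12-week visit as lost would include women removed for pregnancy, as IV.C requires, and score the protocol's own exclusion as infeasibility.

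**Conclusion.** The facts are as described, but no change to the plan is warranted. The missing attrition definition is detail that analysts of a two-arm pilot would fill sensibly. They would report losses by arm among randomised women at the 12-week visit within its 2-week window, show pregnancy exclusions separately, and describe the observation arm by Part B enrolment. Arm, enrolment and attendance are all recorded.

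Read that way, lifestyle attrition together with the adherence counts speaks to the intervention. Observation attrition speaks to running the trial with part of the arm paid. It would be too strong to say that only the lifestyle figure is informative.

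The 2.5 to 15 point distortion arises only if the arms are pooled, which no section proposes, and only under assumed uptake and payment effects. For weight, the largest false-positive rate in the illustrations is 6.2%, on a secondary outcome in a trial whose plan admits limited power, and the direction of bias is unknown. Moving the Part B payment would be a trade-off: it would match the arms more closely but might lose control-arm weights and paired surveys. Keeping it as it stands is defensible.

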#### D. Description, Risks and Justification of Procedures and Data Collection Tools:

Study procedures are listed below with related risks and justifications.

Main study:

Surveys: We will orally read survey questions to participants and responses. It may be tiring answering questions in our survey. Also, a participant may feel discomfort answering questions of a personal nature, but subjects can always choose not to answer any question.

Anthropometric measurements: We will measure heights and weights using WIC clinic scales and stadiometers. Participants may feel uncomfortable being weighed.

Lifestyle coaching: At the baseline, 4 and 8 week visits, intervention-arm participants will receive lifestyle coaching from WIC staff as described above. Participants may feel uncomfortable filling in the HeartSmartMoms survey, or answering lifestyle questions with the WIC staff. They may feel uncomfortable setting lifestyle behavior goals. Given that WIC staff will be using a patient-centered approach with motivational interviewing, this discomfort should be reduced. Motivational interviewing is a critical aspect of behavior change in weight loss intervention focused on behavior change.

Using a pedometer: Intervention participants will be asked to use a pedometer – clicked onto their clothing. Participants may find using a pedometer uncomfortable. They may find discomfort in seeing their step counts. We will educate participants on how to use the pedometer, to help ensure comfort. We will also counsel participants on how step counts can be helpful and to set realistic goals using this device.

Exercise: Lifestyle coaching will encourage exercise because it is an important part of weight loss interventions. There are risks associated with exercise. Exercise may cause sweating, fatigue, or

feeling out of breath. It is also possible that participants could develop soreness or injuries from increased exercise. Exercise can rarely cause abnormal heartbeats, chest pain, passing out, heart attack, stroke, or death, which are extremely rare events.

Weight Loss: The intervention will encourage weight loss. With a reduction in caloric intake, participants may experience hunger and fatigue. Sometimes people experience constipation, nausea, abdominal discomfort or diarrhea from diet changes. Headaches, trouble sleeping, changing in mood or psychological stress can also occur. Weight loss may occur too rapidly resulting in weakness and fatigue. Lifestyle coaching will counsel on gradual weight loss. WIC staff will be checking weights in intervention participants every 4 weeks and can counsel participants if weight loss is too rapid. The most serious but very rare side effect of reduced calorie diets is gallstone formation, which usually only occurs with extremely low fat diets, which will not be recommended in the intervention. WIC educators will have the support of WIC RDs for all participants. Study investigators are experienced in appropriate weight loss.

Changes in WIC benefits: Being asked to come in to WIC more frequently and having your WIC benefits given to you in 1 month amounts may cause you and your family stress and added burden.

Confidentiality: The Principal Investigator and her staff will take all reasonable measures to protect the confidentiality of each subject's records and data. Subject data will be referenced by number only. Research data on paper will be kept in a secured file cabinet in a secured office area. Research data kept online will be kept secure and confidential through password protection. Data will be stored in RedCap and on a secure University server. Data kept on HeartSmartMoms will have participant ID number, but no other identifiable information.

Substudy:

Surveys: We will orally read survey questions to participants and responses. It may be tiring answering questions in our survey. Also, a participant may feel discomfort answering questions of a personal nature, but subjects can always choose not to answer any question.

Confidentiality: The Principal Investigator and her staff will take all reasonable measures to protect the confidentiality of each subject's records and data. Subject data will be referenced by number only. Research data on paper will be kept in a secured file cabinet in a secured office area. Research data kept online will be kept secure and confidential through password protection. Data will be stored in RedCap. Audiorecordings will be stored on a secure University server. Data kept on HeartSmartMoms will have participant ID number, but no other identifiable information.

**E. Potential Scientific Problems:** This is a pilot intervention that has never been trialed before. It is based on information gathered from WIC staff, WIC leadership, WIC clients and is based on evidence from other settings. However, because it has never been trialed before, we may find significant feasibility and acceptability issues leading to significant attrition, making it impossible to complete Aim 2 for the main and substudies. Given that this is a feasibility trial, with a small sample

size, we may also not have enough power to detect differences between intervention and control participants if the differences are small.

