## Study procedures:

### Main study:

In this randomized controlled study participants will be randomly assigned to either an observation group (control) or a Lifestyle group (intervention). Both groups will receive the following:

1. Two visits to the WIC office for data collection as described below (Baseline and at 12 weeks).
2. Study visit reminder calls and/or texts either or both ~1 week and ~1-3 days before baseline and the 12 week study visit.
3. A small gift (less than \$5 in value) at the baseline visit.

For each subject, the time from enrollment to study completion will be approximately 12-20 weeks, depending on timing of scheduling of the visits.

Baseline and 12 week study visits and parameters to be measured on all participants:

At the baseline study visit, we expect data collection to take < 30 minutes. We will collect data using a survey and anthropometric measurements.

- **Survey:** We will orally administer the survey (Appendix B) to participants to avoid literacy issues that are common in low-income populations. Survey questions will include the following:
  - a. Demographics: Maternal age, education level, race, ethnicity, marital status, employment status, number of children, age of youngest child (months), ages of children at home, and acculturation level. To measure acculturation, we will use an adapted version of the Spanish and English language-use subscales of the Bidimensional Acculturation Scale for Latinos. Each subscale contains 5 items about language use, with responses ranging from never (1) to always (5).
  - b. We will also ask about smoking, formula and breastfeeding, and whether the mother has been or is diabetic or prediabetic, mother's weight before her recent pregnancy, and whether she is currently participating in any weight loss programs or is pregnant.

- c. Contact information: We will ask for her name, address, phone numbers, email address, and contact information for someone we can call if we cannot reach the participant. We will ask her to identify the number she wants to receive texts and the email address where we send the Facebook invite, if she is in the Lifestyle group.
- **Anthropometrics:** Weight and height measured twice using WIC scales and stadiometer.

At the 12 week study visit, we expect data collection to take about 20 minutes, collecting anthropometric measurements and some survey data.

**Anthropometrics:** Weight and height measured twice using WIC scales and stadiometer.

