**Survey:** We will orally administer the survey (Appendix J) to participants to avoid literacy issues that are common in low-income populations. Survey questions will include the following:

- a. Demographics: Maternal employment status.
- b. We will also ask about smoking, formula and breastfeeding, and whether the mother has been or is diabetic or prediabetic, and whether she is pregnant.

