## **F. Data Analysis Plan:**

Aim 1: To evaluate the feasibility and acceptability of a multi-component novel weight loss intervention delivered in a WIC setting to a population of low-income, predominantly racial/ethnic minority, obese, postpartum women.

- The RA will transcribe the audiorecorded responses to open-ended questions posed to participants and WIC staff on acceptability. We will use a thematic analytic approach to analyze the data. After reading and discussing all responses amongst team members, we will create a list of codes. We will then use an iterative process to revise codes as needed and identify main themes. We will use a software program (Atlas.ti) for coding. We will assess the ease of recruiting women for the study (number enrolled/number approached) and attrition from the study. We will also calculate the intervention adherence measures, including number of women who received the entire intervention, number of women who came to all visits, participation in self-monitoring, use of phone coaching, and use of the Facebook page. For the Facebook page, we will count the number of posts/individual and categorize the content based on the type of content we see.

Aim 2: To evaluate differences in diet, physical activity, self-efficacy, eating stimulus, and weight change between intervention and control participants to determine preliminary intervention efficacy over a 12-week period.

- We will conduct a univariate analysis of variables to evaluate for baseline group differences, distributions, and outliers for demographic, lifestyle and infant feeding variables. Student t-tests will be used to test for differences between intervention and control groups in change in weight (baseline to 12 wks) and in lifestyle habits using a 2-tailed  $\alpha=0.05$  for statistical significance. [name] will conduct the analysis in consultation with the Child Health Research Biostatistical Core.

Sample Size: This is a feasibility trial, hence, we will not be powered to detect all clinically significant findings. The sample size was chosen based on the sample needed to achieve Aim1. The sample size is 40 (20 intervention and 20 control). We are asking for a sample size in the application up to 80 in case we have a large number of individuals enroll but not participate in the substudy. Given that this is a feasibility trial, we are unsure how difficult recruitment will be.

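### Section IV.D names physical harms of the exercise and diet change, but the protocol body describes no harm question put to both arms and no by-arm comparison of week-12 infant feeding

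*Combined protocol and SAP*

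**What the plan says.** Section IV.D describes the risks of what the lifestyle arm is encouraged to do. On exercise it says "It is also possible that participants could develop soreness or injuries from increased exercise", and it adds breathlessness, fatigue and, as extremely rare events, cardiac problems, stroke and death. On diet and weight loss it says "Sometimes people experience constipation, nausea, abdominal discomfort or diarrhea from diet changes", and it adds hunger, headaches, disturbed sleep, mood change, psychological stress, over-rapid weight loss and, very rarely, gallstones.

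The 12-week survey for all main-study participants (section IV.C, Appendix J) is described as covering employment status and "smoking, formula and breastfeeding, and whether the mother has been or is diabetic or prediabetic, and whether she is pregnant". The baseline survey likewise says "We will also ask about smoking, formula and breastfeeding". In the overview table of data collection, the rows "Breastfeeding history" and "Health questions" are marked at baseline and 12 weeks.

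The outcomes in section IV.A are recruitment, attrition, adherence, weight change, interviews, and the substudy diet, activity and psychosocial measures. None is a harm measure.

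Section F names infant feeding once, in a univariate analysis to "evaluate for baseline group differences, distributions, and outliers for demographic, lifestyle and infant feeding variables". The between-group t-tests cover change in weight and lifestyle habits. Section G says that a feasible and acceptable result would support evaluation on a larger scale.

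**The concern.** The plan lists specific harms that it considers possible, for an intervention that section IV.E says has never been tried, and then describes no way to compare their frequency between arms. Symptoms such as soreness, fatigue, headache and poor sleep are also plausible in untreated postpartum women, so reports from one arm alone cannot be interpreted. Spontaneous reports would probably come mostly from the lifestyle arm, which is seen and contacted more often. Attrition is counted, but recording the reason is not mentioned, so a woman who leaves because of an injury would look like any other dropout.

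Infant feeding raises a related question. One text-message topic is eating fewer calories, and the women are 3 to 12 months postpartum at entry. Whether feeding changes differently by arm is a natural question, and the answers will already have been collected.

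At stake is the evidence behind the step to a larger study, which would be taken without planned between-arm information on harm.

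**Working it through.** The plan states no harm rate or precision target, so there is no figure of its own to reproduce. The check has two parts.

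**1. What is asked, of whom, and how it is used**

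- Exercise symptoms and injuries (section IV.D): no question is described in either arm at week 12.
- Gastrointestinal symptoms, headache, fatigue, gallstones (section IV.D): no question is described in either arm at week 12.
- Sleep: asked in HeartSmartMoms at baseline, 4 and 8 weeks, lifestyle arm only.
- Over-rapid weight loss: weights are checked at 4 and 8 weeks for counselling, lifestyle arm only. Weight is measured in both arms at week 12, but is planned only as an efficacy outcome.
- Psychological stress: the Perceived Stress Scale is given in both arms of the substudy, at baseline only.
- General experience of the programme: week-12 interview, lifestyle women in the substudy only.
- The table row "Health questions": the only content that the text gives for it is diabetes or prediabetes and pregnancy.
- Infant feeding: asked in both arms at both visits. The only analysis that names it is the univariate check tied to baseline differences.

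Count of named exercise or diet symptoms with a described week-12 question in both arms: 0. Count of between-arm harm comparisons in section F: 0.

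**2. What the added data could show**

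Inputs: 20 per arm (section F), or 40 per arm if the permitted 80 enrol and split evenly. Event and feeding rates are assumptions, because the documents give none.

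Upper one-sided 95% bound when no event is seen in n women, 1 − 0.05^(1/n):
- n = 20: 1 − 0.05^(1/20) = 13.9%
- n = 40: 1 − 0.05^(1/40) = 7.2%

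Chance of seeing at least one event in 20 women, 1 − (1 − p)^20:
- p = 1%: 18%
- p = 5%: 64%
- p = 10%: 88%

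Half-width of the 95% interval for a difference in two proportions, both assumed to be 50%, 1.96 × √(2 × 0.25 / n):
- n = 40 per arm: 1.96 × √0.0125 = 21.9 points
- n = 20 per arm: 1.96 × √0.025 = 31.0 points
- n = 10 per arm: 1.96 × √0.05 = 43.8 points

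The last line matters because continued breastfeeding can be assessed only in women breastfeeding at baseline. Their number is not given; 10 per arm is an illustration.

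For an assumed harm rate of 5% against 25%, power is about 42% at 20 per arm and 71% at 40 per arm. Common symptoms would probably be observed, but a formal test would be weak.

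**The case against.** A reader might infer that no visit asks about any named harm. The documents do not support that. The app asks about sleep, interim weights are checked, and the interviews give lifestyle women room to mention discomfort. Appendix J and the full content of the health questions cannot be seen, so an item may exist there. What stands is narrower: none of the described items is both comparative and about these harms.

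A reader might also infer that infant feeding will be analysed only at baseline, so that a fall in breastfeeding would go unreported. Section F also mentions distributions and outliers, which need not be limited to baseline, and the data will exist by arm. What is missing is a stated comparison. Nor do the documents say that the programme reduces breastfeeding: section IV.D does not list it as a risk, and treating it as a possible harm is an inference made here.

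The strongest objection is that this is a feasibility pilot whose next step is another study, where harms could be measured with useful precision. It already excludes women with health problems affecting eating or exercise, advises consulting a provider before exercising, and counsels gradual weight loss. Added data would be imprecise, self-reported by women who know their arm, and missing for dropouts, when section IV.E anticipates that attrition may be significant. All of that is fair. It limits the claims that the data could support and argues for descriptive reporting. It does not remove the value of asking both arms the same questions, since section G makes this pilot the basis for deciding whether to go further.

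**Conclusion.** The point holds in a limited form. The protocol names harms, but its body describes no symptom or injury question common to both arms and no by-arm comparison of week-12 feeding. As described, the plan would yield no planned comparative harm data. This rests on the protocol body and data-collection table; it would be partly answered if Appendix J already contains such items.

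The gain from closing the gap is real but modest. Zero events in 20 women would exclude only rates above about 14%, or about 7% with 40 women. A feeding difference would carry roughly ±31 points at 20 per arm and ±44 points at 10 per arm, assuming 50% rates. Events that section IV.D calls extremely rare cannot be assessed at this size. The change is worth making because it costs little, not because the pilot could establish safety.

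**What to change.** - **Week-12 survey.** Unless Appendix J already has it, add a short yes/no list of the events named in section IV.D, covering the time since baseline, and whether care was sought. Use identical wording in both arms.
- **Withdrawals.** Ask women who leave for their reason where they can be reached, because a week-12 survey alone misses them.
- **Section F.** Report event counts and withdrawal reasons by arm. Add a descriptive by-arm summary of week-12 feeding: the proportion still breastfeeding among those breastfeeding at baseline, and change in formula use, each with a 95% confidence interval.
- **Stated limits.** Say that these results are descriptive, give the expected precision, and note that extremely rare events cannot be assessed.

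The cost is about two minutes of an existing oral survey, a small survey amendment, brief contact with withdrawing women and one table. The feeding summary needs no new data. The main downside is that participants know their assignment, so the coached arm may report symptoms more readily; the report should say so. No clinical rule changes.
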